9.2 Sample Size and Randomization

Treatment Assignment Procedures

Statistical Power:

Utilizing effect sizes and statistical variance from the Stage 1 MB-BP clinical trial showed an increase of MAIA from baseline of mean 22.6 (SD=6.5) to mean 26.3 (SD=6.0) at 6-month follow-up, demonstrating a 3.7 increase in MAIA score ($p < 0.001$). Power analyses using the T statistic and non-centrality parameter, with alpha (two-tailed) set at 0.05 and beta at 0.2, shows with a MAIA increase of 3.7 in MB-BP vs. control, sample size requirements are 46 per group. With DASH diet score increasing from 2.78 (SD=0.61) at baseline to 3.37 (SD=0.81) at 6-month follow-up in the Stage 1 MB-BP study in the 67% of participants with a low DASH score (< 5.5), demonstrating a DASH diet score increase of 0.59 ($p < 0.001$). Using an effect size of 0.5, power analyses using the T statistic and non-centrality parameter

suggest that, with alpha (two-tailed) set at 0.05 and beta at 0.2, a sample size of 33 per group will be sufficient.

Using simulations from Fritz and MacKinnon,²⁴⁸ for 80% power to detect a mediated effect when effect of exposure on mediator, and mediator on outcome, is of small to medium strength (standardized Cohen's d effect sizes of 0.26-0.39 each), based on Sobel first-order test, we will need 90 participants. Given that 67% of Stage 1 participants had DASH diet score <5.5, recruiting a sample size of 160 participants across the UH2 and UH3 phases (Figure 1), this would allow for 107 participants with low DASH diet to be included in primary mediation analyses with DASH diet score as the outcome. Stage 1 effect sizes on DASH diet score were large Cohen's d (d=0.82). Effect sizes on the primary self-regulation outcome was medium (MAIA Cohen's d=0.59). Assuming associations between the MAIA and DASH diet score are in the small to medium range, the study should be adequately powered for mediation analyses. Please note that Stage 1 analyses also demonstrated significant improvements in other health behaviors, including alcohol consumption and physical activity following the MB-BP intervention. Secondary analyses will evaluate impacts of MB-BP on these health behaviors, but are not adequately powered for mediation analyses due to the lower proportion of participants that do not adhere to these behavioral AHA guidelines (i.e. approximately 15% of participants do not comply to AHA alcohol guidelines, and 32% do not adhere to physical activity guidelines in our Stage 1 sample).

The fMRI imaging analyses (n=24 per group) should be adequately powered, based on power calculations shown in the MINDFUL-PC study below and by power calculations outlined in the fMRI study protocol and MOP. To achieve this, we estimate having to enroll up to 60 eligible study participants into the fMRI study.

For fMRI self-regulation neural targets, resting State Functional Connectivity (rs-FC) will be expressed as correlation coefficients, transformed using Fisher's z-transformation for analysis. rs-FC will be obtained at two time points (baseline: T1; post-training: T2) for participants and controls. We will use a mixed effects model with baseline rs-FC as an additional predictor for the change outcome. There are two elements to the hypotheses – the determination of the significance of the change within group and the comparison of the change in the treatment group compared to the control group. For the comparison in change between treatment and control group, with a mixed analysis of variance (within-subjects rs-FC at T1 and T2, and between-subjects according to intervention; sample size, total n = 48, 24/group), we are able to detect an ES of 0.3 between the two treatment groups with 81.3% power (and an ES of .21 with 81.3% power for within-group mindfulness effect; an ES of 0.23 with 87.7% power for an interaction of treatment and time), with two-sided tests at alpha=0.05. Thus is reasonable power to detect small- to moderate-size differences in BOLD.²⁴⁹

Our calculations assume drop-out rates will average around 10-15% across each group, with the control group exhibiting the highest rates of withdrawal and loss to follow up. These estimates are based on the Stage 1 and 2a MB-BP trials in the UH2 phase.

Randomization procedure: Please see Section 3 (study design) above.

Blinding protocol: Please see Section 3 (study design) above.

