1. STUDY OBJECTIVES

1.1 Primary Objective

1. **Impacts of MB-BP on Primary Self-Regulation Targets:** Identify the impacts of MB-BP vs. enhanced usual care on the primary self-regulation target, specifically an assay of self-related processes (MAIA) described in Table 1. We hypothesize that MB-BP will significantly improve the MAIA in directions of better self-regulation, compared to control.
 - a. Secondary analyses will evaluate impacts on secondary self-regulation targets including an assay of emotion regulation (DERS), and cognitive processes (SART), described in Table 1.
 - b. Exploratory analyses will evaluate engagement of MB-BP vs. enhanced usual care with triangulated self-regulation target assays described in **Table 1** such as emotion regulation and stress (Pittsburgh Stress Battery, Perceived Stress Scale), self-related processes (Heart Beat Detection Task, Interoceptive Awareness fMRI Task), and cognitive processes (Mindful Attention Awareness Scale). Measures such as the neuroimaging Interoceptive Awareness fMRI Task will replicate assays in the MINDFUL-PC study.
2. **Self-Regulation Targets as Mediators of MB-BP Effect on Medical Regimen Adherence and Health Behavior Change:** Evaluate the degree to which the engagement of MB-BP with self-regulation targets translates into improved prehypertension/hypertension medical regimen adherence, specifically for the Dietary Approaches to Stop Hypertension (DASH)-consistent diet. We hypothesize that MB-BP will increase the DASH diet score compared to control, in participants with low DASH diet adherence at baseline (DASH diet score <5.5), and that the self-regulation primary outcomes in Aim 1 are significant mediators.
3. **Further develop an MB-BP therapist manual and training program, including procedures for training, supervising, and evaluating therapists.** The PI will implement training he receives from the University of Bangor in the United Kingdom in May 2018 to implement the Mindfulness-Based Interventions Teacher Assessment Criteria (MBI-TAC) for MB-BP instructors, which is the most respected quantitative and qualitative tool developed to provide feedback for enhancing MBI teacher effectiveness, and establishing teacher certification.¹⁻³

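### Section 9.2 states 10-15% dropout, but its 46 per group (MAIA) and 33 per group (low-DASH) are numbers analysed; at 50 enrolled per arm, completer t-test power is about 76-79% and 73-76%, not 80%

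*Combined protocol and SAP*

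**What the plan says.** Section 9.2 uses a two-sided alpha of 0.05, a beta of 0.2 and a t-test with a noncentrality parameter.

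- **MAIA (primary outcome, Section 9.5.1).** Stage 1 went from a mean of 22.6 (SD 6.5) to 26.3 (SD 6.0) at 6 months. From this, "with a MAIA increase of 3.7 in MB-BP vs. control, sample size requirements are 46 per group".
- **DASH score.** The Stage 1 data are given as "With DASH diet score increasing from 2.78 (SD=0.61) at baseline to 3.37 (SD=0.81) at 6-month follow-up", "in the 67% of participants with a low DASH score", a change of 0.59. The sizing sentence begins "Using an effect size of 0.5, power analyses using the T statistic and non-centrality parameter" and concludes that "a sample size of 33 per group will be sufficient". Section 1.1 restricts the DASH hypothesis to participants with a baseline score below 5.5.
- **Mediation.** 90 participants are needed. 160 recruited across the UH2 and UH3 phases are expected to give 107 with a low DASH score.
- **fMRI.** 24 per group are needed, with up to 60 enrolled in total.
- **Dropout.** After these calculations, the section says: "Our calculations assume drop-out rates will average around 10-15% across each group".

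Enrolment is 50 per arm (Sections 3 and 6.2.4). Section 9.1 plans a GEE on repeated measures, following intention to treat. Section 3 calls DASH the primary adherence outcome; Section 9.5.2 places it among the secondary outcomes.

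**The concern.** A reader of Section 9.2 will take it that 80% power holds after 10-15% dropout. No step in the section carries 46 or 33 up to an enrolment figure. Fifty per arm is only slightly above 46, and the low-DASH share of 50 is almost exactly 33. If 46 and 33 are already the numbers needed at analysis, the stated power and the stated dropout cannot both hold at 50 per arm on the section's own test.

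What is at stake is an accurate statement of power for the primary outcome and for the DASH comparison within UH3. Two smaller gaps affect the same calculations: the DASH effect of 0.5 has no unit, and within-group Stage 1 changes serve as between-group differences without comment.

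**Working it through.** **Inputs (all Section 9.2 unless noted).** MAIA difference 3.7, SDs 6.5 and 6.0. DASH effect 0.5, SDs 0.61 and 0.81, Stage 1 change 0.59. Low-DASH share 67%. Dropout 10-15%. Enrolment 50 per arm (Sections 3 and 6.2.4). Two-sided alpha 0.05, power 80%, two-sample t-test by noncentral t.

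**1. Standard deviations.** SD = √((SD₁² + SD₂²)/2).
- MAIA: √((6.5² + 6.0²)/2) = 6.255, so d = 3.7/6.255 = 0.59.
- DASH: √((0.61² + 0.81²)/2) = 0.717, so the Stage 1 d = 0.59/0.717 = 0.82.

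Section 9.2 reports these same standardised effects (0.59 for MAIA, 0.82 for DASH), which supports these SDs.

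**2. The plan's own sample sizes.**
- MAIA, d = 0.592: n = 45.8 per group, i.e. the stated 46.
- DASH, 0.5 points, d = 0.5/0.717 = 0.697: n = 33.3 per group, matching the stated 33 (power 79.7% at 33).

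Neither needs a dropout term to reproduce.

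**3. Loss that 50 per arm can absorb.**
- MAIA: 1 − 46/50 = 8%.
- Low-DASH: 50 × 0.67 = 33.5 expected against 33 needed, so almost none.

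For comparison, inflating 46 gives 46/0.90 = 51.1 (52) and 46/0.85 = 54.1 (55) per arm. Fifty is below both.

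**4. Numbers left after 10-15% dropout.**
- MAIA: 50 × 0.90 = 45; 50 × 0.85 = 42.5.
- Low-DASH: 33.5 × 0.90 = 30.2; 33.5 × 0.85 = 28.5.

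**5. Completer t-test power (n rounded down).**

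| Comparison | n per group | Power | Difference detectable at 80% |
|---|---|---|---|
| MAIA, 3.7 points | 45 | 79.3% | 3.74 |
| MAIA, 3.7 points | 42 | 76.4% | 3.87 |
| DASH, 0.5 points | 30 | 75.7% | 0.53 |
| DASH, 0.5 points | 28 | 72.7% | 0.55 |
| DASH, 0.59 points | 30 | 88.0% | as above |
| DASH, 0.59 points | 28 | 85.6% | as above |

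**6. The other two calculations.**
- Mediation: 107 × 0.90 = 96.3 and 107 × 0.85 = 91.0, against 90 needed.
- fMRI: 48/60 = 0.80, a 20% allowance.

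Both cover the stated dropout.

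**7. What baseline adjustment could recover (assumption).** The documents give no baseline-to-follow-up correlation r. If adjustment multiplies the residual variance by (1 − r²), 80% is restored at r = 0.14 (n = 45) to 0.29 (n = 42) for MAIA, and at r = 0.32 (n = 30) to 0.40 (n = 28) for DASH.

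**8. Unit of the DASH effect.** A two-group Cohen's d of 0.5 needs 63.8, i.e. 64 per group, so it cannot produce 33. Of the two-group readings, 0.5 score points with SD 0.717 does. A one-sample d of 0.5 also gives about 33 (33.4), but the text says per group.

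**The case against.** **Scope of the dropout sentence.** It follows the fMRI paragraph and might cover only that sub-study. But it speaks of the calculations generally and of each group, and bases the rates on the earlier MB-BP trials; fMRI already has its own larger margin. The wording is slightly ambiguous, but the natural reading includes MAIA and DASH.

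**Dropout is partly handled.** This stands. The mediation and fMRI numbers absorb it, and a reader should not infer that Section 9.2 ignores dropout throughout.

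**The completer t-test is not the planned analysis.** This stands as a limit. MAIA and diet are measured at baseline, 10 weeks and 6 months (Section 6.1), late assessments are accepted (Section 3), and modest correlations would close the gap. The figures above are therefore not the trial's power under GEE. But Section 9.1 states no power for the GEE, and intention to treat does not supply outcomes for people lost to follow-up.

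**The DASH assumption is already cautious.** This stands in part: at 0.59 points, power after dropout is 86-88%. The 67% share is also not exact; the binomial SD of the low-DASH count in 50 people is √(50 × 0.67 × 0.33) = 3.3, similar in size to the 3-5 lost to dropout.

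**A stronger reading of the unit.** "Stage 1 effect sizes on DASH diet score were large" refers to Cohen's d, so a reader might take 0.5 as a Cohen's d too and infer that the DASH comparison is severely underpowered. The documents do not support that: such an effect needs 64 per group and is incompatible with the stated 33. The unit is a missing clarification, not evidence of a large power deficit.

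**Conclusion.** The inconsistency is real and limited to the MAIA and UH3-only DASH t-tests. At 50 per arm and 10-15% dropout, the section's own test falls about 1-4 points short of 80% for MAIA and about 4-7 points short for low-DASH at 0.5 points. A reader might infer that the trial is seriously underpowered for its primary outcome; the documents do not support that, since at 10% dropout the MAIA shortfall is one person per group.

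The result rests on Stage 1 SDs carrying over, the 67% share holding in both arms, completers only, and 0.5 meaning score points. It also inherits the plan's use of Stage 1 pre-post changes as MB-BP versus control differences, which assumes no change in controls. Figure 1 is not shown in this copy and may give retention or analysed numbers that reconcile part of this.

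**What to change.** Keep enrolment at 50 per arm and restate the MAIA and DASH parts of Section 9.2, for example:

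> The 46 (MAIA) and 33 (low-DASH) per group are numbers analysed. With 50 enrolled per arm and 10-15% dropout, about 42-45 per group will be analysed for MAIA (completer t-test power about 76-79% for a difference of 3.7, SD 6.255). About 28-30 per group with baseline DASH below 5.5 will be analysed for DASH (about 73-76% for 0.5 DASH points, SD 0.717 [sponsor to confirm unit and SD]; about 86-88% for 0.59 points). Both differences come from within-group changes in Stage 1 and assume no change in controls. The planned repeated-measures GEE may give more power.

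If the Stage 1 baseline-to-follow-up correlation is available, state it with the power it implies. If Figure 1 gives analysed numbers, cite them here. The mediation and fMRI calculations need no change on this point.

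**Cost:** a text edit and one sponsor confirmation. No extra participants and no change to the analysis; the stated power becomes slightly less favourable.

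### The fMRI power text credits to mindfulness a within-group change whose stated power matches a time effect pooled over both arms, with no treatment contrast

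*Combined protocol and SAP*

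**What the plan says.** The fMRI part of Section 9.2 (Sample Size and Randomization) sets out the rs-FC analysis. Both arms are scanned at T1 (baseline) and T2 (post-training), which Section 6.2.3, item 34, places at baseline and 10 weeks. The model is stated: "We will use a mixed effects model with baseline rs-FC as an additional predictor for the change outcome". Two hypothesis elements follow: "the determination of the significance of the change within group and the comparison of the change in the treatment group", where the comparison is between treatment and control.

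Three power figures are given for a two-group, two-time mixed ANOVA ("sample size, total n = 48, 24/group"), "with two-sided tests at alpha=0.05":

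- between groups: "we are able to detect an ES of 0.3 between the two treatment groups with 81.3% power"
- within group: "an ES of .21 with 81.3% power for within-group mindfulness effect"
- interaction: "an ES of 0.23 with 87.7% power for an interaction of treatment and time"

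The section does not say whether both elements must be met, whether the within-group element is descriptive, or which element supports a conclusion about MB-BP. Objective 1b in Section 1.1 frames the exploratory assays, fMRI included, as MB-BP against enhanced usual care. Section 6.2.3 refers to a separate fMRI protocol for details.

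**The concern.** A change from T1 to T2 is not in itself an effect of the intervention. It also contains whatever would have changed anyway over 10 weeks and on a second visit to the scanner. Controls are scanned on the same schedule so that this shared part can be subtracted. A hypothesis about the significance of the within-group change skips the subtraction, and the label given to its power figure attributes the change to mindfulness in advance.

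At stake is what the sub-study may conclude. If the within-group element were significant and the between-arm comparison were not, Section 9.2 has no rule to stop the first being described as a mindfulness effect on the neural target.

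**Working it through.** **Inputs from Section 9.2.** N = 48 in total, 24 per arm; m = 2 time points; two-sided alpha 0.05; effect sizes 0.21 (within), 0.23 (interaction) and 0.30 (between), taken as Cohen's f.

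**Assumptions.** The correlation rho between T1 and T2 is not given; I use 0.5 and vary it. The documents give no size for any retest drift, so drift is shown as a range.

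**Step 1: reproduce the plan's figures.** For the time main effect and the interaction, lambda = f² × N × m / (1 − rho), with F on 1 and 46 df.

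- Within, f = 0.21, rho = 0.5: lambda = 0.0441 × 96 / 0.5 = 8.47; power 81.29% (stated 81.3%).
- Interaction, f = 0.23, rho = 0.5: lambda = 0.0529 × 96 / 0.5 = 10.16; power 87.69% (stated 87.7%).

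Both match under one assumption. The within-group figure is then the time main effect averaged over all 48 participants.

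**Step 2: could it be the MB-BP arm alone?** With two time points, f = 0.21 is a mean change of 2 × 0.21 = 0.42 SD of a single measurement. In SDs of the change score this is 0.42 / √(2(1 − rho)). The one-sample t test with n = 24 (noncentral t, 23 df) gives:

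| rho | MB-BP arm alone, n=24 | Interaction (f=0.23), n=48 |
|---|---|---|
| 0.3 | 38% | 75% |
| 0.5 | 50% | 88% |
| 0.7 | 72% | 98% |

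To reach 81.3%, the single-arm test needs rho above 0.7. The interaction power would then exceed 98%, not 87.7%. The single-arm reading therefore does not fit the paragraph's own companion figure; the pooled reading does.

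**Step 3: what shared drift does.** Let both arms drift by d SDs of the change score, with no MB-BP effect. The pooled time test has lambda = 48d² (F, 1 and 46 df). The MB-BP-arm test has noncentrality d√24 (t, 23 df). In these units the results do not depend on rho.

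| d | Pooled: lambda | Pooled: P(significant) | MB-BP arm: noncentrality | MB-BP arm: P(significant) | Between arms |
|---|---|---|---|---|---|
| 0.2 | 1.92 | 27% | 0.98 | 16% | 5% |
| 0.3 | 4.32 | 53% | 1.47 | 29% | 5% |
| 0.4 | 7.68 | 77% | 1.96 | 47% | 5% |

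The between-arm test of change stays at 5% because the shared drift cancels. A 20,000-run simulation at d = 0, 0.2 and 0.42 gave 4.9% to 5.0%.

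**Side observation.** The between-group figure uses lambda = f² × N × m / (1 + rho). At rho = 0.5, lambda = 0.09 × 96 / 1.5 = 5.76 and power is 65.2%. At rho = 0, lambda = 8.64 and power is 82.1%. The stated 81.3% thus needs rho near 0, while the other two figures need 0.5. The correlation should be stated and made consistent.

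**The case against.** The strongest reply is that the right analysis is already there. Section 9.2 names the comparison of change between arms, fits a baseline-adjusted model, scans both arms twice and powers treatment by time. Objective 1b is comparative. All of this stands, and it is why the repair needs only wording.

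The two elements can also be read jointly: change occurs, and it differs from control. If both had to be met, the false-positive rate could not exceed the 5% of the between-arm test, whatever the drift. The text permits this reading but does not state it, and powering the first element separately under its own label points away from it.

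Three stronger readings are tempting, and the documents do not support them:

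- A reader might infer that a within-group result alone will be presented as efficacy. No section says so.
- A reader might infer that significance in MB-BP will be set against non-significance in control. Section 9.2 plans a direct comparison of change, so error rates for that procedure do not describe this plan.
- A reader might add regression to the mean as a source of drift. Participants are selected on blood pressure (Sections 4.1 and 6.2.1), not on rs-FC, so this has little support here.

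The stakes are also limited. The primary outcome is MAIA (Section 9.5.1). The fMRI assay is exploratory in Section 1.1, although Section 9.5.2 lists the fMRI task among the secondary outcomes. The separate fMRI protocol was not available for this review and may already restrict the inference.

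**Conclusion.** The point holds as a matter of labelling and of a missing rule. Section 9.2 lists within-group significance as a hypothesis element and powers it as an effect of mindfulness. The stated power fits a time effect pooled over MB-BP and control, which contains no treatment contrast; for the MB-BP arm alone the power is about 50%. For a shared drift of 0.2 to 0.4 SD of the change score and no MB-BP effect, the pooled test would be significant in 27% to 77% of trials and the MB-BP-arm test in 16% to 47%, against 5% for the comparison between arms.

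The identification as a pooled effect and the 50% figure rest on rho = 0.5, which is inferred from the match of two stated figures. The drift range is assumed, and nothing in the documents shows that rs-FC drifts by that much. The conclusion concerns what this sub-study may claim, not the primary result.

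**What to change.** In Section 9.2:

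1. State that any rs-FC change is attributed to MB-BP only on the basis of the baseline-adjusted comparison of change between arms, which the section already names.
2. Report within-arm changes as estimates with confidence intervals.
3. Delete the power statement for the within-group effect, or relabel it as the time effect pooled over both arms.
4. State the T1–T2 correlation behind all the power figures.

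Check that the separate fMRI protocol says the same.

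The cost is wording and one favourable power figure. The stated 87.7% for treatment by time at n = 48 is kept, and no scan, participant or model changes.

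### The three fMRI power figures in Section 9.2 do not fit one scan-to-scan correlation: where two of them reproduce, between-group power is about 65%, not 81.3%

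*Combined protocol and SAP*

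**What the plan says.** Section 9.2 plans resting-state connectivity at two scans: "rs-FC will be obtained at two time points (baseline: T1; post-training: T2) for participants and controls". The planned model has change as the outcome and adjusts for the baseline value. The power statement that follows is attached to a mixed analysis of variance ("sample size, total n = 48, 24/group", "two-sided tests at alpha=0.05"). It opens with the comparison of change between arms and gives three figures:

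- between groups: "we are able to detect an ES of 0.3 between the two treatment groups with 81.3% power"
- within group: "an ES of .21 with 81.3% power for within-group mindfulness effect"
- interaction: "an ES of 0.23 with 87.7% power for an interaction of treatment and time"

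The section concludes that there is "reasonable power to detect small- to moderate-size differences in BOLD". Earlier it says "The fMRI imaging analyses (n=24 per group) should be adequately powered", citing calculations from another study and from a separate fMRI protocol and manual of procedures. It does not say what ES denotes or what correlation between T1 and T2 was assumed. Elsewhere in the section, a Cohen's d of 0.82 is called large and one of 0.59 medium.

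**The concern.** One outcome measured twice in one design has one T1-T2 correlation. In a mixed analysis of variance, a higher correlation raises power for the time effect and the interaction and lowers it for the group main effect. Three power figures for the same 48 people must therefore agree on a single value, and these do not appear to.

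Two labels also look wrong. The figure given first is a group main effect, which averages the baseline and post-training scans, although the sentence announces a comparison of change. The within-group figure is described as the mindfulness effect but seems to count the controls.

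At stake is how the fMRI results are read. If between-group power is overstated and the detectable difference in change is understated, a null imaging result could be taken as stronger evidence against a moderate effect than 24 per group can give.

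**Working it through.** **Inputs from Section 9.2.** N = 48 (24 per group), m = 2 scans, two-sided alpha 0.05; ES 0.3, 0.21 and 0.23 with stated powers 81.3%, 81.3% and 87.7%.

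**Assumptions.** ES is Cohen's f. The correlation rho is not stated, so it is solved from the stated powers and varied.

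**Formulas.** Noncentral F with 1 and 46 degrees of freedom; the 5% critical value is 4.05.

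- Between groups: lambda = f² × N × m / (1 + rho)
- Time and interaction: lambda = f² × N × m / (1 − rho)

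**Step 1: reproduce the plan's figures at rho = 0.5.**

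- Within: 0.21² × 96 / 0.5 = 8.47, power 81.3%. Matches.
- Interaction: 0.23² × 96 / 0.5 = 10.16, power 87.7%. Matches.
- Between: 0.3² × 96 / 1.5 = 5.76, power 65.2%. Stated 81.3%; does not match. A simulation of 40,000 trials gives 65.1%.

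**Step 2: look for a single rho.**

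| rho | Between, f = 0.3 | Within, f = 0.21 | Interaction, f = 0.23 |
|---|---|---|---|
| 0.02 | 81.3% | 53.0% | 60.6% |
| 0.3 | 71.4% | 67.3% | 75.1% |
| 0.5 | 65.2% | 81.3% | 87.7% |
| 0.7 | 59.8% | 95.7% | 98.1% |

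Solved separately, the within and interaction figures each give rho = 0.500 and the between figure gives 0.020. At rho = 0.5, 81.3% between-group power needs f = 0.364.

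**Step 3: other routes to 81.3% at rho = 0.5.** One-sided testing gives 76.4%, N = 60 gives 75.1%, three scans 70.3% and four scans 73.0%. If 0.3 were a rounded value just under 0.35, power would be 78%. With baseline adjustment, lambda = f² × N / (1 − rho²) on 1 and 45 degrees of freedom: 0.09 × 48 / 0.75 = 5.76, power 65.1%. That model reaches 81.3% only at rho = 0.7 (0.09 × 48 / 0.51 = 8.47).

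**Step 4: what the interaction figure means.** In a 2 × 2 design the interaction moves each cell mean by a quarter of the difference in change, so that difference is 4f = 4 × 0.23 = 0.92 raw SD. At rho = 0.5 the SD of change is √(2 × 0.5) = 1 raw SD, so it is also 0.92 SD of change. A two-sample t-test on change with 24 per group gives the same 87.7%.

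**Step 5: detectable difference in change at 80% power, 24 per group.** Unadjusted, it is 0.83 SD of change, whatever rho is. With the planned baseline adjustment it is about 0.83 × √(1 − rho²) raw SD:

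| rho | Detectable difference (raw SD) | Power for 0.5 raw SD |
|---|---|---|
| 0.5 | 0.72 | 50% |
| 0.6 | 0.66 | 56% |
| 0.7 | 0.59 | 66% |
| 0.8 | 0.50 | 81% |

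**Step 6: the within-group figure.** The 81.3% in Step 1 uses all 48 people. For the 24 in MB-BP, lambda = 0.21² × 48 / 0.5 = 4.23 on 1 and 23 degrees of freedom, and power is 50.5%.

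**The case against.** The strongest reply is that rho and the metric are inferred, and that the plan names a baseline-adjusted model. Under that model with rho = 0.7, f = 0.3 gives 81.3%, while the mixed-ANOVA powers for the other two effects rise to 96% and 98%, so all three stated powers would be met or exceeded. This stands to the extent that 65% is conditional on rho = 0.5 and is not the only possible value. It does not rescue the text: Section 9.2 attaches the figures to a mixed analysis of variance, two of them match to the printed decimal at 0.5, and the adjusted model at 0.5 also gives 65%. Reaching 81.3% requires a different model and a different correlation for one figure of the three.

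A reader might infer that 24 per group can detect only large effects. The documents do not support that flatly. With baseline adjustment the detectable difference is 0.72 raw SD at rho 0.5 and 0.59 at rho 0.7, which runs from between the section's own medium and large down to its medium.

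A reader might also infer that the imaging sample size rests on the wrong figure, or that the claim of adequate power must be struck out. Neither follows. The figure for the contrast of interest, the interaction, is arithmetically correct, and adequacy is also referred to calculations in a separate fMRI protocol that is not available here.

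Finally, the reach is limited. Imaging is an optional substudy with its own consent. The fMRI task is exploratory in Section 1.1 and secondary in Section 9.5.2, and the MAIA primary outcome does not depend on it.

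**Conclusion.** The concern holds in bounded form. If ES is Cohen's f and the analysis is the mixed analysis of variance that Section 9.2 names, no single T1-T2 correlation gives all three stated powers. At 0.5, which reproduces two of them exactly, between-group power is overstated by about 16 percentage points (81.3% against 65.2%). The repeated 81.3% may be a copying slip, but the documents do not show this.

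Two labelling faults accompany it: the first figure belongs to a main effect and not to the comparison of change, and the within-group figure counts both arms. The small-to-moderate description is unsupported at that correlation, because f = 0.23 there is a 0.92 SD difference in change. How far it misses under the planned model depends on a correlation that the section does not give. The consequence is confined to the exploratory or secondary fMRI analyses.

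**What to change.** In Section 9.2:

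- State the effect-size metric, the assumed T1-T2 correlation and the model behind each figure.
- Name the difference in change between arms as the target contrast.
- Restate the between-group figure (if rho is 0.5: about 65% at f = 0.3, or f of about 0.36 for 81%), or drop it.
- Label the within-group figure as using all 48 participants, or restate it for 24 (about 50% at f = 0.21).
- Replace the small-to-moderate wording with the detectable difference in change at 80% power: about 0.83 SD of change unadjusted, or, with baseline adjustment, about 0.72, 0.66, 0.59 and 0.50 raw SD at rho 0.5, 0.6, 0.7 and 0.8.
- Reconcile these figures with the separate fMRI protocol and manual of procedures.

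The cost is wording only, with no added scans or participants; some of the stated figures become less favourable.
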